1.0 RESPONSIBLE PARTIES INVOLVED IN THE STUDY

A list of all responsible parties, such as medical monitors, and contract research organizations, who are involved in the operations of the study is filed in the Sponsor’s Trial Master File. The names of the individuals and corresponding phone numbers who should be contacted regarding the conduct of the study, adverse events, safety issues, and complaints are provided in the Site Investigator File.

2.0 SYNOPSIS

Title:	A Study to Evaluate the Safety and Effectiveness of Microwave Ablation in Patients with Hepatocellular Carcinoma in Korea
Protocol Number:	NEU_2017_01
Products:	Neuwave Medical’s Certus 140™ Ablation System used with Certus LK Probes (LK15, LK15XT, LK20 and LK20XT) or PR Probes (PR15, PR20, PR15XT and PR20XT). These are collectively described as “study devices.”
Regulatory Classification:	Registered Devices used in a clinical trial 
 • Certus LK Probes (LK15, LK15XT, LK20, or LK20XT) or PR Probes (PR15, PR20, PR15XT, or PR20XT) (Class 2) • Neuwave Medical’s Certus 140™ Ablation System (Class 3)
Control:	N/A
Device Indication:	The NeuWave Medical’s Certus 140™ 2.45 GHz Ablation System and Accessories are indicated for the ablation (coagulation) of soft tissue in percutaneous, open surgical, and in conjunction with laparoscopic surgical settings. Certus 140™ Ablation Probes are designed for use only with the Certus 140™ 2.45 GHz Ablation System. The Certus 140™ 2.45 GHz Ablation System is not indicated for use in cardiac or endometrial procedures. The study devices will be utilized as described in the IFU. In this study, the study devices will only be used for the ablation or coagulation of liver tissue in percutaneous settings.
Objective(s):	To evaluate the outcomes of microwave ablation of patients with hepatocellular carcinoma (HCC) of ≥ 2 cm and up to 5 cm. 
 • Primary Endpoint: Technical Success, defined as complete tumor ablation with adequate or insufficient ablation margin, based on contrast-enhanced MRI and CT scans immediately following the ablation procedure. • Secondary Endpoints: 
 • Primary Technique Efficacy, defined as complete tumor ablation with adequate or insufficient ablation margin, based on contrast-enhanced MRI and CT scans follow-up at 1 month after the ablation procedure; • Local tumor progression (LTP) rate, evaluated at 1, 3, 6, 9, 12, 18, 24, 30 and 36 months after the ablation of the index tumor;

	
 • Primary efficacy rate, defined as the percentage of target tumors successfully eradicated following the ablation procedure; • Secondary efficacy rate, defined as the percentage of tumors that have undergone successful repeat ablation following identification of local tumor progression; • Progression free survival and overall survival rates at 36 months after the ablation procedure; • Rate of adverse events reported through 3 months and cumulatively through study completion; • Quality of Life, as measured by VAS pain score, EORTC QLQ-C30 and EORTC QLQ-HCC18, before the ablation procedure and at each post-ablation visit; • Health economics associated with the ablation procedure: complete procedure time, ablation time, no. of ablations, length of stay, no. and types of probes used.

Study Design:
	
This prospective, single-arm single center study will provide clinical data using Neuwave Medical's Certus 140™ 2.45GHz Ablation System used with Certus LK Probes (LK15, LK15XT, LK20, and LK20XT) or PR Probes (PR15, PR20, PR15XT, and PR20XT) (study devices). Individuals who undergo microwave ablation of liver tumors in accordance with their institution's standard of care (SOC) for ablation, and who meet study entry criteria, may be enrolled.
 
The enrollment for the study will continue until 30 eligible subjects complete the 3-month visit after ablation (Visit 4) for the primary effectiveness and safety analysis.
 
The subjects will be followed for up to 36 months after the ablation procedure for safety and ablation outcomes.

Number of Sites:
	
One (1) site in Korea

Sample Size:
	
Total planned: 30 subjects who complete 3-month visit after ablation (Visit 4):


Diagnosis/Criteria for Inclusion:
	
 1. Confirmed hepatocellular carcinoma, tumor ≥ 2 cm and up to 5 cm, single location, BCLC Stage A based on imaging (CT Scan or MRI or ultrasound) and biopsy confirmation in accordance with their institution's standard of care (SOC) procedure; 2. Primary hepatocellular carcinoma or recurrent hepatocellular carcinoma which was previously treated with ablation or surgical resection only; 3. Scheduled for microwave ablation of the liver; 4. Performance status 0-2 (Eastern Cooperative Oncology Group classification); 5. Functional hepatic reserve based on the Child-Pugh score (Class A or B); 6. ASA score ≤ 3; 7. Given voluntary, written informed consent to participate in this study and has authorized the transfer of his/her information to the Sponsor, and willing to comply with study-related evaluation and treatment schedule; and 8. At least 19 years of age.

Diagnosis/Criteria for Exclusion:	
 1. Active (subject currently receiving systemic treatment) bacterial infection or fungal infection; 2. Systemic administration (intravenous or oral) of steroids, including herbal supplements that contain steroids, within 30 days prior to the study procedure; 3. Chemotherapy or radiation therapy for hepatocellular carcinoma may not be performed for 30 days prior to the study procedure; 4. Subject with implantable pacemakers or other electronic implants; 5. Planned/ scheduled liver surgery. 6. Subject with a platelet count of less than 50,000/mm³; 7. Subject with an INR greater than 1.5; 8. Subject with renal failure on renal dialysis; 9. Scheduled concurrent procedure other than microwave ablation in the liver; 10. Pregnant or breastfeeding; 11. Physical or psychological condition which would impair study participation; 12. Participation in any other clinical study concurrently or within the last 3 months; 13. The subject is judged unsuitable for study participation by the Investigator for any other reason; or 14. Unable or unwilling to attend follow-up visits and examinations.
Study Duration:	Planned Recruitment Period: 9-12 months Follow-up Period: up to 36 months
Safety:	All adverse events (AEs) will be recorded and reported appropriately throughout the study.
Statistical Methods:	
Categorical variables will be summarized descriptively by frequencies and associated percentages. Continuous variables will be summarized descriptively by number of subjects, mean, standard deviation, median, minimum, and maximum. Confidence intervals will also be provided for procedure-related variables.
 
The number and percentage of subjects achieving Technical Success will be summarized and an exact 95% confidence interval will be estimated. A similar summary will be provided for Primary Technique Efficacy, as well as for the primary and secondary efficacy rates as previously defined.
 
Local tumor progression rates at 1, 3, 6, 9, 12, 18, 24, 30 and 36 months will be estimated using the Kaplan-Meier method and 95% confidence intervals will be provided.
 
The number and percentage of subjects experiencing adverse events (AEs) will be summarized at the preferred term level using the Society of Interventional Radiology (SIR) clinical practice guidelines for event categorization.
 
Two analyses of study data are planned. The first will occur after 30 subjects have completed the 3-month visit and is intended to provide an initial estimate of device effectiveness for Technical Success as well as to summarize the peri-operative out to 3-month post-operative safety

	
profile of subjects undergoing microwave ablation. There are no plans to use the results of the first analysis for the purpose of stopping the study early. The second analysis will occur after all subjects have completed study participation.

--	--

Table 1: Schedule of Events

Visit No. Visit	Visit1: Screening	Visit2A Pre-Ablation	Visit2B Ablation	Visit2C Post-Ablation	Visit3 1 month	Visit4 3 months	Visit5 6 months	Visit6 9 months	Visit7 1 year	Visit8 18 months	Visit9 2 years	Visit10 30 months	Visit11 3 years	USV Unscheduled Visit ⁸
Interval Windows	Within 5 weeks before ablation	-2 to 0 days	Day 0= Ablation of index tumor	0 to 4 days	1 month (+/- 14 days) after ablation	3 months (+/-28days) after ablation	6 months (+/-28 days) after ablation	9 months (+/-28 days) after ablation	12 months (+/-28 days) after ablation	18 months (+/-28 days) after ablation	24 months (+/-28 days) after ablation	30 months (+/-56 days) after ablation	36 months (+/-28 days) after ablation	NA
Study Activity														
Informed Consent	X													
Demographic Information	X													
Medical/Surgical History	X													
Inclusion/Exclusion Criteria	X													
VAS Pain Score	X			X	X	X	X	X	X	X	X	X	X	
EORTC QLQ-C30	X			X	X	X	X	X	X	X	X	X	X	
EORTC QLQ-HCC18	X			X	X	X	X	X	X	X	X	X	X	
CT Scan (Liver)	X		X	X	X	X	X	X	X	X	X	X	X	
MRI (Liver) ⁹	X		X	X	X	X	X	X	X	X	X	X	X	
Ultrasound (Liver) ⁹	X		X	X	X	X	X	X	X	X	X	X	X	
Coagulation Test ¹¹	X		X	X	X	X	X	X	X	X	X	X	X	
Liver Function Test ¹²	X		X	X	X	X	X	X	X	X	X	X	X	
Renal Function Test ¹³	X		X	X	X	X	X	X	X	X	X	X	X	
Complete blood count (CBC) ¹⁴	X		X	X	X	X	X	X	X	X	X	X	X	
Alpha-fetoprotein (AFP) ¹⁵	X		X	X	X	X	X	X	X	X	X	X	X	
PIVKA-II ¹⁶	X		X	X	X	X	X	X	X	X	X	X	X	
Pregnancy Test ¹⁷	X		X	X	X	X	X	X	X	X	X	X	X	
Tumor Size, Type and Location	X		X	X	X	X	X	X	X	X	X	X	X	
BCLC Staging	X		X	X	X	X	X	X	X	X	X	X	X	
ECOG Performance Status	X		X	X	X	X	X	X	X	X	X	X	X	
Child-Pugh Score	X		X	X	X	X	X	X	X	X	X	X	X	
ASA Score	X		X	X	X	X	X	X	X	X	X	X	X	
Procedure Details ⁶			X											
Device Accountability			X											

Visit No. Visit	Visit1: Screening	Visit2A Pre-Ablation	Visit2B Ablation	Visit2C Post-Ablation	Visit3 1 month	Visit4 3 months	Visit5 6 months	Visit6 9 months	Visit7 1 year	Visit8 18 months	Visit9 2 years	Visit10 30 months	Visit11 3 years	USV Unscheduled Visit ⁸
Interval Windows	Within 5 weeks before ablation	-2 to 0 days	Day 0= Ablation of index tumor	0 to 4 days	1 month (+/- 14 days) after ablation	3 months (+/-28days) after ablation	6 months (+/-28 days) after ablation	9 months (+/-28 days) after ablation	12 months (+/-28 days) after ablation	18 months (+/-28 days) after ablation	24 months (+/-28 days) after ablation	30 months (+/-56 days) after ablation	36 months (+/-28 days) after ablation	NA
Study Activity														
Length of Hospital Stay		X		X										
Complete Tumor Ablation Evaluation			X		X									
LTP Evaluation					X	X	X	X	X	X	X	X	X	
Follow-up Post-ablation Treatment ⁷					X	X	X	X	X	X	X	X	X	X
Concomitant Medications	X	X	X	X	X	X	X	X	X	X	X	X	X	X
Relevant Concomitant Procedures				X	X	X	X	X	X	X	X	X	X	X
Adverse Event and SAEs ⁶			X	X	X	X	X	X	X	X	X	X	X	X

Notes:

- CT Scan of the liver: For Visit 1, the CT Scan must be performed within 37 days of the visit and the subject does not need to repeat a CT scan of the liver, if the liver CT scan based on SOC was done within 37 days of Visit 1. For Visit 2B/2C, the CT Scan will be done up to 4 days after the completion of the ablation procedure for all subjects, and CT Scan may also be used to guide the ablation procedure for some subjects. For the follow-up Visits 3 to 11, the CT Scan may be done within 14 days prior to the visit.
- MRI of the liver: For Visit 2B/2C, the MRI will be done up to 4 days following the completion of the ablation procedure for all subjects. For Visit 3, the MRI may be done within 14 days prior to the visit. After Visit 3, a MRI may be done once per year of follow-up, if applicable, depending on each subject's condition and based on the clinical judgement of the Investigator (hence, O = optional).
- Ultrasound of the liver: For Visit 1, the planning ultrasound will be done on the day of the visit or up to 7 days prior. For Visit 2B, ultrasound is used to guide the ablation procedure.
- For Visit 1, the laboratory tests must be performed within 37 days of the visit and the subject does not need to repeat the laboratory test(s), if the laboratory test(s) based on SOC was/ were done within 37 days of Visit 1. For the follow-up Visits 3 to 11, the laboratory tests will be done within 14 days prior to the visit.
 - Coagulation Test: Includes PT, APTT, and INR
 - Liver Function Test: Includes AST, ALT, GGT, albumin, indirect, direct and total bilirubin, and total protein.
 - Renal Function Test: Includes BUN, Creatinine and electrolytes (sodium, potassium and chloride).
 - Complete Blood Count (CBC): Includes differential cell count and platelet count.
- Pregnancy test: For women of child bearing potential only.
- Procedure Details: Includes complete procedure time, ablation time, anatomical location of ablation, procedure performed, no. of probe placement attempts per probe, no. of ablations, and ablation maximum power and time settings. Some of the ablation procedure details will be provided to the site via a report generated from NeuWave Medical's Call Home Database. The study site will review the report and enter the procedure details into the clinical database, as applicable.
- Follow-up Post-Ablation Treatment: If applicable.

8. Adverse Event and SAEs: Subjects will be assessed for safety from day of ablation through the 3-year follow-up. All AEs and SAEs will be reported from the day of the ablation up to 3 months after the ablation procedure. Expected serious adverse device effects (SADE), unexpected serious adverse device effects (USADE), life-threatening events, or events that result in death, and all SAEs with definite, possible, probable or unknown relationship to the study device or study procedure, will be reported from day of the ablation through the 3-year follow-up.
9. Unscheduled visits are only for those which are procedure, device or disease related.

NOTE:

- Subjects who have recurred at the target lesion or progressed with a new lesion following the first ablation, and are treated with any treatment post progression will be followed every 6 months (+/-28 days) from the day of the first ablation as a clinic visit or, if clinic visit is not possible, a phone contact visit (if a clinic visit is not possible). This will be called a "Reduced Follow-Up Schedule."

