11.5 VISIT 3 (1 MONTH AFTER ABLATION)

The following data will be collected during this follow-up visit:

- Quality of Life questionnaires: VAS pain score, EORTC QLQ-C30 and EORTC QLQ-HCC18;
- Evaluation of ECOG Performance Status;
- MRI and CT scans of the liver (within 14 days prior to the visit):
 - Complete tumor ablation evaluation, including LTP;
 - Indication for repeat ablation (if applicable);
- Laboratory tests (within 14 days prior to the visit):
 - Alpha-fetoprotein (AFP) test;
 - Prothrombin Induced by Vitamin K Absence or Antagonist-II (PIVKA-II);
 - Coagulation test (PT, APTT, and INR);
 - Liver function test (AST, ALT, GGT, albumin, indirect, direct and total bilirubin, total protein);
 - Renal function test (BUN, Creatinine and electrolytes (sodium, potassium, and chloride));
 - Complete Blood Count (CBC) (differential cell count and platelet count);
- Follow-up post-ablation treatment (if applicable);
- All Adverse Events and SAEs (if applicable);
- Any update to concomitant medications and procedures.

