11.11 INDEPENDENT REVIEWER (IR)

An Independent Reviewer, from the site in Korea, will be utilized in this clinical trial in order to

reduce the variability between investigators in assessing the CT images (and as needed, MRI and Ultrasound) and to minimize potential bias. The Independent Reviewer will review all CT scans taken throughout the study (including at screening) using the images stored in the hospital's database and without referring to the radiology imaging report in order to avoid influence in the assessment. All images will be taken in accordance with the hospital's Standard of Care. At baseline, the independent reviewer will confirm the presence of one lesion, and its location, size, and BCLC stage.

According to the standard practice at the site in Korea, the independent review will classify the ablation as:

- complete tumor ablation with adequate margin
- complete tumor ablation with insufficient margin
- incomplete tumor ablation.

This assessment will be done for the scans taken following the ablation procedure (Visit 2, for technical success) and at the 1-month visit (Visit 3, for technical efficacy).

At all post-ablation follow up visits, the central reviewer will assess recurrence of the target lesion, progression, meaning a new lesion(s), or lack thereof. If there is a progression or recurrence, the central reviewer will again assess number of lesions, location, size and BCLC stage.

The assessment by the independent reviewer will only be used for the purpose of statistical analysis while the assessment by the investigators will be used for the treatment of the subjects in the study as well as reported in the analysis.

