15.3 INTERVAL WINDOWS

Subjects are scheduled for 9 post-ablation visits under this protocol. For summarization of selected endpoints at post-ablation time points, the following windows will be defined around each scheduled visit to identify the corresponding measurement to be summarized for that visit:

- Visit 3 – 1 month (± 14 days) post ablation;
- Visit 4 – 3 months (± 28 days) post ablation;
- Visit 5 – 6 months (± 28 days) post ablation;
- Visit 6 – 9 months (± 28 days) post ablation;
- Visit 7 – 12 months (± 28 days) post ablation;
- Visit 8 – 18 months (± 28 days) post ablation;
- Visit 9 – 24 months (± 28 days) post ablation;
- Visit 10 – 30 months (± 56 days) post ablation; and
- Visit 11 – 36 months (± 28 days) post ablation.

In cases where multiple measurements fall into a given window, the measurement that is closest in time (number of days) to the scheduled measurement will be utilized in all analyses. Subject and site compliance with the protocol specified visit windows will be monitored throughout the study and the final SAP may be revised to expand the windows as necessary so as not to exclude relevant subject measurements that may be near the existing windows.

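### Can a protocol-compliant Visit 3 scan be dated so early that Primary Technique Efficacy stops being a 1-month result?

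*Combined protocol and SAP*

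**What the plan says.** The Table 1 schedule in Section 2.0 sets Visit 3 at "1 month (+/- 14 days) after ablation", and Section 15.3 repeats the window as "1 month (± 14 days) post ablation". The Table 1 notes let imaging run ahead of the clinic visit: "For the follow-up Visits 3 to 11, the CT Scan may be done within 14 days prior to the visit", and "For Visit 3, the MRI may be done within 14 days prior to the visit". Section 11.5 says the same of both modalities, "MRI and CT scans of the liver (within 14 days prior to the visit", and lists what is read from these scans: "Complete tumor ablation evaluation, including LTP". For the post-ablation time point, "the CT Scan will be done up to 4 days after the completion of the ablation procedure for all subjects", and the MRI has the same 4-day limit.

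Two sections bear on which date places a scan. Section 11.11 has the independent reviewer classify the ablation on scans labelled by visit, "at the 1-month visit (Visit 3, for technical efficacy". Section 15.3 describes its windows as the means of picking the measurement to summarise for a visit. It resolves multiple measurements by closeness to the scheduled day, and it lets the final SAP widen the windows if relevant measurements fall just outside. It applies to selected endpoints, which it does not list. Neither section names the governing date.

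**The concern.** Primary Technique Efficacy is defined at 1 month and is meant to be distinct from Technical Success, which is read on scans from the first few days. If a scan carries its visit's label, an image taken shortly after ablation could be reported as the 1-month finding, and two endpoints intended to be about a month apart could rest on images only days apart. The planned count, percentage and exact interval would not reveal this.

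If a scan is instead placed by its own date, a fully compliant scan can fall before the Section 15.3 window. Section 15.8.5 allows no imputation, so that subject might have no 1-month result. The 1-month local tumor progression evaluation uses the same scan, and Section 15.8.3 restricts that analysis to subjects with an observation at the time point. Each reading has an awkward consequence, and the text does not choose between them.

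**Working it through.** The plan states no figure for the earliest scan date, so there is none to reproduce. The check is date arithmetic.

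**Inputs.** Visit window ±14 days (Table 1, Section 15.3). Scan lead 0 to 14 days before the visit (Table 1 notes, Section 11.5). Post-ablation scans on days 0 to 4 (Table 1 notes). The length of a month, M, is not defined; 28, 30 and 31 days are tried as assumptions.

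**Earliest compliant scan.** Earliest visit = M − 14. Earliest scan = M − 14 − 14 = M − 28.

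| M (assumed) | Section 15.3 window | Earliest scan |
|---|---|---|
| 28 | day 14 to 42 | day 0 |
| 30 | day 16 to 44 | day 2 |
| 31 | day 17 to 45 | day 3 |

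Whatever the month length, the scan can be 28 days early against a margin of 14, and 28/14 = 2.

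**When a scan precedes the window.** This happens exactly when days the visit is early + days of scan lead > 14.
- Visit on or after the 1-month point: never.
- Visit 7 days early: leads of 8 to 14 days, 7 of the 15 whole-day leads.
- Visit 14 days early: leads of 1 to 14 days, 14 of 15.

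**Share of permitted timings.** Permitted scan days number 29 + 14 = 43, and 14/43 = 32.6% lie before the window. Counting combinations instead, there are 29 visit days × 15 leads = 435. For a visit e days early, e of the leads put the scan before the window, so the count is 1 + 2 + … + 14 = 105, and 105/435 = 24.1%. A scan on day 4 or earlier with M = 30 needs days early + lead ≥ 26. That gives 3 + 2 + 1 = 6 combinations, and 6/435 = 1.4%. These are shares of what is permitted and not forecasts; the documents hold no scan-timing data.

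**Effect on precision if scan date governed.** Take 30 subjects for illustration. Sections 15.6 and 15.7 make 30 a minimum number of 3-month completers, not the size of the Full Analysis Set. Weighting all combinations equally, 30 × 105/435 = 7.2 scans would precede the window; round up to 8, leaving 22. With no failures the exact 95% lower limit is 0.025^(1/n): 88.4% at n = 30 and 84.6% at n = 22, a loss of 3.8 percentage points. If visit date governed, none of these scans would be dropped.

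**The case for a change.** The best argument for a change is that a single SAP sentence would settle the matter at almost no cost, before anyone has seen when scans were taken. Widening the window, as Section 15.3 permits, is not a clean cure: covering every compliant Visit 3 scan would mean opening it at about day 2 (30-day month), which overlaps the Technical Success scans. A table of scan days beside the endpoint, or a repeat of the summary restricted to scans inside the window, would also show readers something the planned summary hides.

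The arithmetic behind this stands, and so does the observation that no governing date is named. What does not stand is the step to a defect. It cannot be said that an early scan will count as the 1-month result: Section 11.11 points to the visit label, while the wording of Section 15.3, being about measurements, points to the scan date. Nor is either convention shown to give a wrong answer. Nothing in the documents indicates that an earlier scan would be classified differently, or in which direction. The extra rows would add reporting; they would not correct a stated rule. With no hypotheses or significance levels (Sections 15.4 and 15.5), a later choice of convention puts no error rate at risk.

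**Conclusion.** No change to the plan follows. The allowances do stack to 28 days, but what is missing is a date convention of the kind analysts normally write into a SAP. Section 15.1 promises a detailed SAP before database lock, and Section 15.3 already commits to monitoring window compliance and to adjusting windows. Letting imaging precede the clinic visit is a fair scheduling trade-off, and it leads outside the window only when the visit is early as well.

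The exposure is narrow. The overlap with the day 0 to 4 scans takes 6 of 435 permitted combinations (1.4%, 30-day month assumed). Under equal weighting of combinations, the cost of the stricter reading is about 3.8 percentage points on an exact lower limit, in an illustration with 30 subjects and no failures. Only Primary Technique Efficacy and the 1-month local tumor progression result are touched, both secondary and descriptive; Technical Success is unaffected. This conclusion rests on scan dates being available with the images, and on the SAP author stating which date is used, as ordinary practice would have it. Actual scan timing is unknown from the documents.
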